#### **4.2.1.5 Overall Survival**

OS will be measured for each subject from the date of the first dose of study drug until the recorded date of death or last follow-up. Subjects who are still alive will be censored on the date of last follow-up. Every effort will be made to follow subjects for OS after they discontinue the study.

#### **4.2.2 Subject Evaluation & Statistics**

The Intent-To-Treat (ITT) Population for clinical efficacy is defined as all subjects who receive at least one dose of study drug or RT.

The Per-Protocol (PP) Population for clinical efficacy is defined as all subjects who received at least 75% of the scheduled doses of the study drug and RT over the first 2 cycles, as well as, respective disease assessments, without major protocol violations.

The analysis will be based on both ITT and PP populations.

Tumor Response will be summarized and analyzed descriptively for each cohort and analysis population.

Tumor response rates will be assessed overall and for each cohort and tabulated with the 95% confidence intervals assuming binomial distribution.

For time-to-event analyses, Kaplan-Meier methodology will be implemented to estimate the median duration of response, median PFS, and median OS at Weeks 12 and 18.

### **4.3 Antitumor Immunity**

#### **4.3.1 Endpoints & Assessment Methods**

Exploratory immunologic objectives will be assessed from peripheral blood and tumor biopsy samples according to the schedule in Section 3.2 to assess the influence of ipilimumab and nivolumab plus RT on assays, which may include but may not be limited to the following:

- Lymphocyte phenotype using markers such as ICOS, PD-1, and CD25;
- Quantities of myeloid-derived suppressor cells (MDSCs), defined as CD14+HLA-DRlow cells;
- Antibody and functional T cell responses to tumor associated antigens (i.e., NY-ESO-1) for relevant subjects;

---

CONFIDENTIAL

- Serum cytokine levels such as TNF-alpha, IFN-gamma, IL-1beta, IL-2, IL-4, IL-5, IL-6, IL-8, IL-10, IL-12, and TGF-beta;
- Serum and plasma microparticle and exosome nanoFACS and proteomic profiles;
- T cell repertoire diversity in peripheral blood and tumor.

Immunologic characteristics will be summarized descriptively. Antibody, T cell phenotype, and functional T-cell responses will be assessed. Antibody responses will be measured using ELISA and a positive antibody response will be defined as extrapolated reciprocal titers > 100 post treatment. Intracellular cytokine staining will be utilized to assess CD4+ and CD8+ T cell responses. Samples collected after treatment will be considered positive for response if they are higher than baseline values by at least 3 standard deviations. Therefore, for each subject, the standard deviation of the pre-treatment at two separate time points (using 6 replicates each) will be computed, and a positive will be defined as greater than 3 times this value and greater than 0.1% after 10-day in vitro stimulation.

Additional investigational methods may be used to characterize and measure components of the immune response based upon the latest available technology.

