Adverse Events Assessment	X	X	X	X	X	X	X	X	X	X d	X	
Laboratory Measurements & Assays												
Serum Pregnancy Test e	X									X d,e	X e	
Urine Pregnancy Test (collected pre-dose) e		X		X		X			X	(Q6W) d,e		
Chemistry (Na, K, Cl, CO 2 , BUN, creat., gluc., Ca, Mg, total prot., alb., Tbili., AST, ALT, ALP, LDH; blood drawn before dosing) g	(-14 to 0) X	X	X	X	X	X	X	X	X	X d,g		
Free T 3 , Free T 4 , TSH; blood drawn before dosing g	(-14 to 0) X	X	X	X	X	X	X	X	X	X d,g		
Amylase, lipase; blood drawn before dosing	(-14 to 0) X	X	X	X	X	X	X	X	X	X d		
Blood Hematology (CBC with differential and platelets; blood drawn before dosing)	(-14 to 0) X	X	X	X	X	X	X	X	X	X d		
Research Blood Draw (60 mL; blood drawn before dosing)		X		X		X						
Tumor Biopsy (optional) c	X	X		X	X	X	X	X	X			

CONFIDENTIAL

Study Section	Screening	Treatment								Final Assessment and Ongoing Treatment/ Assessments d	On Study Follow-up a,e	Post-Study Follow-up (Section 3.1.16)
		Week 1 (Cycle 1)	Week 4 (Cycle 2)	Week 7 (Cycle 3)	Week 10 (Cycle 4)	Week 12	Week 14	Week 16	Week 18			
Study Week												
Study Day	-28 to 0 (or as stated)	1	22 (± 3)	43 (± 3)	64 (± 3)	78 (± 3)	92 (± 3)	106 (± 3)	120 (± 3)	2 weeks (± 3 days) after last study drug	30 (±4), 70 (±4) and 100-107 days after last study drug (AEs and pregnancy tests)	(Starts after completion of 100-day On Study Follow-up) Q12W (± 7 d) for 3 years
Progression and Survival Follow-up												X

Abbreviations: alb. = albumin; ALP = alkaline phosphatase; ALT = alanine aminotransferase; AST = aspartate aminotransferase; Tbili. = total bilirubin; BP = blood pressure; BUN = blood urea nitrogen; Ca = calcium; CBC = complete blood count; Cl = chloride; CO2 = carbon dioxide; creat. = creatinine; CT = computed tomography; d = day(s); DoB = date of birth; ECOG = Eastern Cooperative Oncology Group; eCRF = electronic case report form; gluc. = glucose; Gy = Gray; HR = heart rate; irRECIST = immune-related RECIST; IV = intravenous(ly); K = potassium; mL = milliliter(s); LDH = lactate dehydrogenase; Mg = magnesium; Na = sodium; prot. = protein; Q = every; RECIST = Response Evaluation Criteria for Solid Tumors; RR = respiratory rate; RT = radiotherapy; W = week(s); Q6W = every 6 weeks; Q12W = every 12 weeks

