Note: Additional assessments may be evaluated at the Investigator's discretion and per standard of care. Indicated assessments within this chart define clinical data to be captured in the eCRF. Standard of Care procedures may be used for eligibility assessments, provided they meet the criteria specified in either the inclusion criteria or flowchart.

a Subjects will be followed for 100 days after the last dose of study drug as a part of On Study Follow-up; during this time, all AEs will be collected at 30 (±4), 70 (±4) and 100-107 days.

b Radiotherapy will be delivered by standard or high dose palliative RT as per cohort assignment.

c Tumor biopsies are optional but are encouraged. Biopsies are prohibited from compromising the requirement for at least one measurable lesion not undergoing RT.

d **Final Assessment** will be 2 weeks (± 3 days) after last study drug, followed by On Study Follow-up and Post Study Follow-up. A repeat disease assessment scan is not required at the final assessment visit if a scan was done within the previous 6 weeks before the final assessment visit. Subjects who do not continue treatment with nivolumab after Week 18 do not need to have a repeat pregnancy test (if applicable) at the final assessment if the subject had this assessment at Week 18.

**For those subjects who are continuing on nivolumab after Week 18 at 240 mg every 2 weeks ±3 days**, Study Visits will continue every 2 weeks ± 3 days during treatment, followed by the Final Assessment Visit, On Study Follow-up, and Post Study Follow-up after the last nivolumab treatment.

Per Amendment 5, nivolumab monotherapy continuing after Week 18 may be given as 480 mg every 4 weeks ±3 days, starting on Week 20, followed by Weeks 24, 28, etc.

**For those subjects who are continuing on nivolumab after Week 18 at 480 mg every 4 weeks ±3 days**, Study Visits will continue every 4 weeks ± 3 days during treatment, followed by the Final Assessment Visit, On Study Follow-up, and Post Study Follow-up after the last nivolumab treatment.

Subjects continuing nivolumab monotherapy, subjects who complete study treatment as responders, and subjects who have not progressed (either in irradiated or non-irradiated tumor burden) will have an additional scan (disease assessments by RECIST 1.1/ irRECIST) at Week 24 and subsequent scans Q12W (± 7 days) until progression or start of alternate anti-cancer therapy.

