## 8.6 Exploratory Assessment of Correlative Immunologic Research

Peripheral blood and optional tumor samples (when available) will be collected as outlined in Section 3.2 and banked for testing at the end of the study. Separate instructions will be provided regarding the processing, storage and testing of these samples. Testing may include but may not be limited to the following:

- lymphocyte phenotype using markers such as ICOS, PD-1, and CD25
- the quantities of myeloid derived suppressor cells (MDSCs), defined as CD14+HLA-DRlow cells
- antibody and functional T cell responses to tumor associated antigens (i.e. NY-ESO-1) for relevant subjects
- serum cytokine levels such as TNF-alpha, IFN-gamma, IL-1beta, IL-2, IL-4, IL-5, IL-6, IL-8, IL-10, IL-12, and TGF-beta
- Serum and plasma microparticle and exosome nanoFACS and proteomic profiles
- T cell repertoire diversity in peripheral blood and tumor.

Additional investigational methods will be used to characterize and measure components of the immune response based upon the latest available technology.

---

CONFIDENTIAL

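### Section 4.3.1 takes the T-cell SD from two pre-treatment time points but Section 3.2 schedules one research draw, and the T-cell and antibody positivity rules need a clear baseline term (minor; exploratory endpoint only)

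*Combined protocol and SAP*

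**What the plan says.** Section 4.3.1 (Endpoints & Assessment Methods, Antitumor Immunity) ties sampling to the flowchart: blood and biopsy samples are assessed "according to the schedule in Section 3.2 to assess the influence of ipilimumab and nivolumab plus RT on assays". It then gives two positivity rules.

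- **T-cell response (intracellular cytokine staining).** The first sentence reads: "Samples collected after treatment will be considered positive for response if they are higher than baseline values by at least 3 standard deviations". The next is introduced as its consequence. It says that, for each subject, "the standard deviation of the pre-treatment at two separate time points (using 6 replicates each) will be computed", and that "a positive will be defined as greater than 3 times this value and greater than 0.1% after 10-day in vitro stimulation".
- **Antibody response (ELISA).** "a positive antibody response will be defined as extrapolated reciprocal titers > 100 post treatment".

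In the Section 3.2 flowchart, the row "Research Blood Draw (60 mL; blood drawn before dosing" is marked at Weeks 1, 7 and 12, and its Screening cell is empty. Biopsies are marked at Screening and Week 1 among other visits, but the footnote says "Tumor biopsies are optional but are encouraged".

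Section 8.6 adds no draw. Samples "will be collected as outlined in Section 3.2 and banked for testing at the end of the study", and separate instructions on processing, storage and testing are promised. Sections 4 and 4.3.1 make the objective exploratory and its summaries descriptive.

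**The concern.** These are the plan's only numerical definitions of a positive T-cell or antibody response. The T-cell rule calls for an input that the sampling schedule does not supply. Its two sentences can classify the same subject differently, so laboratories following different sentences could report different results. The antibody rule has no baseline term, although the stated aim is to assess what treatment does.

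With nine subjects planned per cohort, a few misclassified subjects would visibly alter a descriptive responder count. If the rules are settled only after results are seen, the choice can no longer be shown to be independent of the data.

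**Working it through.** The plan states no error rate, assay variability or sample size for this endpoint, so there is no figure of its own to reproduce.

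**1. Count of draws.** Required by Section 4.3.1: 2 pre-treatment time points × 6 replicates = 12 values. Scheduled in Section 3.2: Weeks 1, 7 and 12, of which only Week 1 (pre-dose) precedes treatment, giving 1 × 6 = 6 values. The shortfall is one time point, and with it any between-visit component. Two alternative readings do not close the gap:
- Reading pre-treatment as pre-radiotherapy does not help. RT starts between the first and second immunotherapy doses, and no research draw falls between Weeks 1 and 7.
- Biopsies are optional and a different specimen, so they cannot supply a blood SD for every subject.

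**2. The two T-cell sentences.** Let m be the baseline mean, s the pre-treatment SD and y the post-treatment value.
- First sentence: positive if y ≥ m + 3s.
- Operational sentence, read literally: positive if y > 3s and y > 0.1%.

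For an unchanged subject (y = m) with s above zero, the first is never met. The second is met whenever m > 0.1% and m > 3s, that is, whenever s/m is below one third.

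Illustration with assumed values m = 0.5% and s = 0.05%: 3s = 0.15% and m + 3s = 0.65%. An unchanged value of 0.5% is positive under the operational sentence and negative under the first. At an assumed m = 0.05%, the 0.1% floor makes it negative under both.

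**3. Antibody rule.** For an unchanged titer T > 100, the post-treatment value is T > 100, so the subject is counted as a response.

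**4. What a one-draw SD costs.** This can only be explored under assumptions. Take the rule y ≥ m + 3s and y > 0.1%, normal replicates, y as the mean of 6 post-treatment replicates, and no true change.

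With no between-visit variation and a baseline well above the floor:
- One draw: P(t₅ > 3/√(1/6 + 1/6)) = P(t₅ > 5.20) = 0.17%.
- Two draws, SD over all 12 values: P(t₁₁ > 3/√(1/6 + 1/12)) = P(t₁₁ > 6) = 0.0045%.

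Both are negligible. With assumed baseline 0.5%, replicate CV 10–20% and between-visit CV 10–30%, simulation gives these false-positive rates:

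| How the two-draw SD is formed | One draw | Two draws | Ratio |
|---|---|---|---|
| Over all 12 replicates | 1.1–25.8% | 0.1–9.3% | about 3–11 |
| Within each time point, then pooled | 1.1–25.8% | 0.2–22% | about 1.2–6 |

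At an assumed baseline of 0.08%, the ratio with all 12 replicates is about 1.5–4. At 0.05%, all rates are below 0.1%. Section 4.3.1 does not say which way the two-time-point SD is formed, and the documents give neither CV nor a baseline frequency. The direction (more unchanged subjects called positive) is plausible. The size is not established.

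**The case against.** The strongest reply is that this is an exploratory, descriptive objective in an 18-subject pilot, with antigen-specific assays planned only for relevant subjects. That stands, and it is why the point is minor.

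- **A laboratory rule may exist.** The flowchart notes allow additional assessments at the investigator's discretion, and Section 8.6 promises separate instructions. A reader might infer that no workable T-cell rule exists. The documents do not support that, because those instructions are not among them and may settle it. They would not remove the disagreement between Sections 4.3.1 and 3.2.
- **The intended T-cell rule is clear.** The first sentence does refer to baseline, so it would be wrong to say that the plan leaves baseline out altogether. Read together, the two sentences most naturally mean baseline plus 3 SD. Even so, the sentence that defines the calculation gives a different rule and should be corrected.
- **The titer limit may be a seropositivity cut-off.** Baseline and post-treatment titers could be described side by side under the existing plan. But the text calls the result a response. A baseline condition also has an arbitrary edge: 99 to 101 counts, while a large rise from 150 does not. Listing the titers of subjects above 100 at baseline answers that.
- **The multipliers are not robust.** A reader might infer that one draw raises false positives by a fixed large factor. The working shows that the factor depends on assumed CVs, the assumed baseline and how the SD is formed.

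**Conclusion.** The point holds as a minor one. Three things follow from the text alone: two pre-treatment time points are required and one is scheduled; the operational T-cell sentence conflicts with the one before it; and the antibody rule counts an unchanged titer above 100 as a response. The first rests on reading the research-blood row as marked at Weeks 1, 7 and 12.

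The number of subjects who would be misclassified is unknown without the laboratory's own replicate and between-visit data, and no rate is claimed. Nor do the documents state that two time points were chosen to capture between-visit variation, though a single draw necessarily omits it. Nothing here reaches the primary safety assessment, the efficacy endpoints or the decision to open Cohort B.

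**What to change.** Make three wording changes before the banked samples are assayed.

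1. **SD.** Define each subject's pre-treatment SD from the six Week 1 pre-dose replicates, so that Section 4.3.1 agrees with Section 3.2. State qualitatively in the report that this SD omits between-visit variation and so may call more unchanged subjects positive. Do not print assumed false-positive rates.
2. **T-cell rule.** Replace the operational sentence with: positive = post-treatment mean at least pre-treatment mean + 3 × pre-treatment SD, and above 0.1%.
3. **Antibody rule.** Define a response as a titer of 100 or less at Week 1 pre-dose and above 100 post treatment. Report subjects above 100 at baseline separately, with baseline and post-treatment titers.

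If the separate laboratory instructions already settle any of these, align the protocol text with them.

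No new sampling is needed, because Week 1 pre-dose blood is already scheduled and testing is planned for the end of the study. A second pre-treatment draw is not part of this fix. The cost is the loss of any between-visit information in the SD, which the caveat discloses.

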#### **4.4 Additional Exploration of Immune Response**

The methods used to analyze immune response to cancer antigens used in this study are well established. However, as cellular biology and immune regulation are very active fields of discovery, the opportunity exists to refine and extend the analysis of immune response. Therefore, although most of the blood drawn for the analysis of the immune response is planned for the assays listed, a small part, if still available, may be used to explore other aspects of immunological response. This work may also involve assessing exosomes and markers associated with radiation-induced immunologic cell death, such as expression of calreticulin and extracellular release of HMGB1. There may also be interest in establishing T-cell lines and clones in culture, evaluating tumor antigen-specific immune responses such as those against NY-ESO-1, assessing TCR repertoire diversity, proteomics/seromics analyses, and using samples in collaborations with other investigators and laboratories including those outside of the Ludwig Institute.

## 5 Subject Eligibility

Note: Standard of Care procedures may be used for eligibility assessments provided they meet the criteria specified in either the inclusion criteria or flowchart.

### 5.1 Inclusion Criteria

Eligible subjects **must fulfill** all of the following criteria:

1.	
Histologic diagnosis of stage IV metastatic melanoma, with 1 melanoma lesion that can be safely irradiated and, in the opinion of the radiation oncologist, is of benefit to the subject to irradiate (note: subjects with primary ocular and mucosal melanoma are permitted). Lesions may include, but are not limited to:
 
 
Symptomatic lymphadenopathy;
 
Bothersome cutaneous disease;
 
Hepatic metastases;
 
Pulmonary metastases.
 

2.	
Excluding the lesion intended to undergo radiation, subjects must have at least 1 unresectable, non-bony lesion that is measurable radiographically (based on RECIST 1.1).

3.	
Any number of prior therapies (including none).
 
For subjects who have received prior systemic treatment with CTLA-4, PD-1, and/or PD-L1 therapy, the last monoclonal antibody administration should be no less than 4 weeks prior to start of this protocol therapy and all prior side effects must have resolved to grade 1 or less by the time of the start of this protocol therapy.

4.	
Subjects must have:
 
 
Completed investigational therapy, other immunotherapy, or prior RT at least 28 days before administration of the first dose of study drug(s)
 
Completed chemotherapy or targeted therapy at least 14 days before administration of the first dose of study drug(s)
 
Sufficiently recovered from prior surgery as determined by the treating Investigator.
 
 
Clinically significant toxicity or pharmacodynamic effects experienced during any prior therapy must be resolved or stabilized before the first dose of study drug(s).

5.	
ECOG performance status of 0-1.

6.	
Life expectancy <math>\geq</math> 4 months.

7.	
Screening laboratory parameters:
 
 
White blood cell (WBC) count <math>\geq</math> 2000/<math>\mu</math>L;
 
Absolute neutrophil count (ANC) <math>\geq</math> 1500/<math>\mu</math>L;
 
Platelets <math>\geq</math> 100,000/<math>\mu</math>L;
 
Hemoglobin (Hgb) <math>\geq</math> 9 g/dL;
 
Aspartate aminotransferase (AST) and alanine aminotransferase (ALT) <math>\leq</math> 3 <math>\times</math> upper limit of normal (ULN);
 
Total bilirubin <math>\leq</math> 1.5 <math>\times</math> ULN (< 3 mg/dL for subjects with Gilbert's disease);
 
Serum creatinine <math>\leq</math> 1.5 <math>\times</math> ULN or creatinine clearance (CrCl) <math>\geq</math> 40 mL/min (if using the Cockcroft-Gault formula below):
 

CONFIDENTIAL

	Female CrCl = [(140 - age in years) x weight in kg x 0.85] / [72 x serum creatinine in mg/dL] Male CrCl = [(140 - age in years) x weight in kg x 1.00] / [72 x serum creatinine in mg/dL]
8.	Age ≥ 18 years.
9.	Able and willing to give valid written informed consent.

## 5.2 Exclusion Criteria

Subjects **may not** enter the study if they fulfill any of the following criteria:

1.	Unresolved irAEs following prior biological therapy. Subjects with asymptomatic endocrinopathy may enroll.
2.	Active autoimmune disease or any condition requiring systemic treatment with either corticosteroids (>10 mg daily of prednisone equivalents) or other immunosuppressive medications within 14 days of study drug administration. Inhaled or topical steroids and adrenal replacement doses > 10 mg daily prednisone equivalents are permitted in the absence of active autoimmune disease.
3.	History of motor neuropathy considered to be of autoimmune origin (e.g., Guillain-Barre Syndrome, Myasthenia Gravis).
4.	Other active, concurrent malignancy that requires ongoing systemic treatment or interferes with radiographic assessment of melanoma response as determined by the investigator.
5.	Active brain metastases or leptomeningeal metastases. Subjects with brain metastases are eligible if metastases have been treated and there is no magnetic resonance imaging (MRI) evidence of progression for 4 weeks or more after treatment is complete and within 28 days prior to the first dose of nivolumab administration. There must also be no requirement for immunosuppressive doses of systemic corticosteroids (> 10 mg/day prednisone equivalents) for at least 2 weeks prior to study drug administration.
6.	Known immunodeficiency or HIV, Hepatitis B, or Hepatitis C positivity. Antibody to Hepatitis B or C without evidence of active infection may be allowed.
7.	History of severe allergic reactions to any unknown allergens or any components of the study drugs.
8.	Other serious illnesses (e.g., serious infections requiring antibiotics, bleeding disorders).
9.	Requirement of RT to treat brain metastases or receipt of any non-study systemic therapy for cancer or any other experimental/investigational treatment.
10.	Mental impairment that may compromise the ability to give informed consent and comply with the requirements of the study.
11.	Lack of availability for immunological and clinical assessments or post-study follow-up contact to determine relapse and survival.
12.	Women who are breastfeeding or who are pregnant as evidenced by a positive serum pregnancy test (minimum sensitivity 25 IU/L or equivalent units of HCG) performed within 14 days of the first dose of study drug and by a urine pregnancy test (minimum sensitivity 25 IU/L or equivalent units of HCG) within 24 hours of the first dose of study drug(s).

CONFIDENTIAL

13.	
Females of childbearing potential who are sexually active with a nonsterilized male partner must use 2 methods of effective contraception from screening, and must agree to continue using such precautions for 23 weeks after the final dose of investigational product; cessation of birth control after this point should be discussed with a responsible physician. Periodic abstinence, the rhythm method, and the withdrawal method are not acceptable methods of birth control.
 
[Females of childbearing potential are defined as those who are not surgically sterile (i.e., bilateral tubal ligation, bilateral oophorectomy, or complete hysterectomy) or postmenopausal (defined as 12 months with no menses without an alternative medical cause).]
 
Nonsterilized males who are sexually active with a female partner of childbearing potential must use 2 acceptable methods of effective contraception from Day 1 and for 31 weeks after receipt of the final dose of investigational product.
 
Acceptable methods of effective contraception are described in the following table:
 
  
 Barrier Methods	Intrauterine Device Methods	Hormonal Methods	
   
 Male condom plus spermicide, cap plus spermicide, or diaphragm plus spermicide.	Copper T, or Levonorgestrel-releasing intrauterine system (e.g., Mirena®), also considered a hormonal method.	Implants, hormone shot or injection, combined pill, minipill, or Patch.	
  
	Barrier Methods	Intrauterine Device Methods	Hormonal Methods	Male condom plus spermicide, cap plus spermicide, or diaphragm plus spermicide.	Copper T, or Levonorgestrel-releasing intrauterine system (e.g., Mirena®), also considered a hormonal method.	Implants, hormone shot or injection, combined pill, minipill, or Patch.
Barrier Methods	Intrauterine Device Methods	Hormonal Methods					
Male condom plus spermicide, cap plus spermicide, or diaphragm plus spermicide.	Copper T, or Levonorgestrel-releasing intrauterine system (e.g., Mirena®), also considered a hormonal method.	Implants, hormone shot or injection, combined pill, minipill, or Patch.					
14.	
Any condition that, in the clinical judgment of the treating physician, is likely to interfere with the interpretability of the data or prevent the subject from complying with any aspect of the protocol or that may put the subject at unacceptable risk.
						

